#### **5.10 Lost to Follow-up**

If the investigator has attempted to contact a subject at least three times within 60 days and received no response, the subject may be considered lost to follow-up. The investigator will document that a minimum of three attempts were made to contact the subject, including sending a certified letter if current address is known, prior to exiting the subject from the study.

## 5.11 Subject Confidentiality

All information concerning subjects or their participation in this study will be considered confidential. Only the authorized Sponsor, designated representative personnel, designated consultants and regulatory agencies will have access to these confidential files. Enrolled subjects will be assigned a unique, pseudo-anonymous identifier that will be used to maintain confidentiality of each subject's medical information. Subject names and other protected health information will not be captured on the case report forms. In addition, all patient identifiers except the unique pseudo-anonymous identifier should be redacted from any images or other data submitted from the participating site to the Sponsor or the Sponsor's designated reviewers for analysis.

## 5.12 Schedule of Events and Assessments

Subjects will complete the following visits and assessments as indicated below and in **Table 4**.

### 5.12.1 Baseline

The following baseline data will be collected:

- Medical history
- Medication history
- Pregnancy test (if applicable)
- 12-lead ECG
- Cardiac CT or MRI
- TEE or other imaging modality for exclusion of left atrial thrombus
- NYHA Classification
- Anticoagulation Monitoring: For subjects on dabigatran, perform a PTT and, if required, a thrombin time and for subjects on warfarin, assessment of INR therapeutic levels (maintain as clinically indicated)

### 5.12.2 Procedure

FARAPULSE endocardial ablation procedure patients will undergo anesthesia according to institutional protocol. They will then be prepared in conventional sterile fashion for a cardiac catheterization procedure. Femoral vein access will be obtained via Seldinger technique. Transseptal access to the left atrium will then be obtained using a commercially approved sheath and Brockenbrough needle. The transseptal sheath will then be withdrawn, leaving guidewire access to the left atrium. The FARADRIVE Deflectable Sheath will then be prepared and advanced via guidewire to the left atrium. Commercially approved multielectrode pacing catheters will then be placed in the coronary sinus and right ventricle via conventional technique. A baseline electrophysiological assessment of pulmonary vein connection to the left atrium will be made and documented via commercially approved diagnostic catheter placement in each addressable

pulmonary vein. A baseline 3D electroanatomical map may also be made at the investigator's discretion. The diagnostic catheter will then be removed from the FARADRIVE Deflectable Sheath.

The FARAWAVE Ablation Catheter will then be prepared and advanced over the guidewire to the left atrium. The guidewire will be advanced into a target pulmonary vein, the catheter splines will be deployed by retracting the deployment knob, and the deployed catheter will be advanced to the ostium of the target pulmonary vein. At the investigator's discretion contrast venography may be performed demonstrate placement of the catheter at the ostium. Cardiac pacing capture from the external cardiac stimulator will be obtained via connection to the coronary sinus and right ventricular pacing catheters. Once pacing capture is confirmed, ablation will be performed. Each addressable pulmonary vein will be ablated in turn beginning with placement of the guidewire, deployment of the ablation catheter, confirmation of pacing capture, and ablation. Ablation dose will be selected at the investigator's discretion in accordance with LBL0198.

After ablation of each addressable pulmonary vein, the FARAWAVE Ablation Catheter will be undeployed and removed. A post-ablation assessment of pulmonary vein isolation will be performed as was done pre-ablation.

For a detailed description of procedure workflow refer to LBL0193 (FARADRIVE Deflectable Sheath System), LBL0195 (FARAWAVE Endocardial Catheter Ablation System), and LBL0198 (FARASTAR Endocardial Generator System). Procedural details will be captured on the Procedural Data CRF. The following procedural data will be collected:

- Medications administered
- Pregnancy test (if applicable)
- Pre- and post-ablation 3D electroanatomical maps
- Fluoroscopic examination of diaphragm motion
- Anticoagulation monitoring (ACT for procedural monitoring)
- Adverse Events

### **5.12.3 Pre-Discharge and 7 Day Follow Up**

Prior to hospital discharge (or 7 Day  $\pm$  2 days Follow Up) the following data will be collected:

- Medications including use, changes in or discontinuation of anticoagulation, rate control and/or antiarrhythmic medications
- Cardiac rhythm as determined by a 12-lead ECG
- Cardioversion(s)
- Heart failure status as assessed by NYHA classification

- Anticoagulation Monitoring: For subjects on anticoagulants, assessment of INR/PTT therapeutic levels as applicable/required (maintain as clinically indicated)
- Adverse Events

#### **5.12.4 30 Day Follow-Up**

Discharged subjects will return for an office visit 30 days ( $\pm$  7 days) post-ablation treatment. Subjects that continue to be hospitalized 30 days post-ablation will have their 30-Day Follow-Up assessment performed at discharge. At a minimum, the following data will be collected at the 30 Day Follow-Up visit:

- Medications including use, changes in or discontinuation of anticoagulation, rate control and/or antiarrhythmic medications
- Cardiac rhythm as determined by a 12-lead ECG at the time of the visit
- Cardioversions since last visit
- Heart failure status as assessed by NYHA classification at the time of visit
- Anticoagulation Monitoring: For subjects on anticoagulants, assessment of INR/PTT therapeutic levels as applicable/required (maintain as clinically indicated)
- Any hospital readmissions, including admission and discharge dates, since discharge from the original procedure
- Adverse Events

#### **5.12.5 75 Day Follow-Up**

Subjects will return for an office visit at 75 days ( $\pm$  15 days) post index ablation. At a minimum, the following data will be collected at the 75-day follow-up visit:

- Medications including use, changes in or discontinuation of anticoagulation, rate control and/or antiarrhythmic medications
- Pregnancy test (if applicable)
- Cardiac rhythm as determined by a 12-lead ECG
- Cardiac CT or MRI scan to assess the patency of the pulmonary veins
- 3D electroanatomical remapping procedure to assess electrical isolation of the pulmonary veins. Any electrical gaps may be closed at the investigator's discretion using a commercially approved ablation device. This will consist of placement of catheters in the left atrium via femoral access and transseptal puncture using conventional electrophysiology techniques. Any electrical gaps may be closed at the investigator's discretion using the study device or, if clinically necessary, using a commercially approved ablation device (which constitutes a therapeutic treatment failure).

- An Event Monitor will be provided to be used up to the 12-month follow-up visit for weekly scheduled and ad hoc symptomatic monitoring. Subjects will retain this device through the 12-month follow-up, ECG data from this monitor will be analyzed by a contract core lab. Investigational sites will be provided with the Event Monitor device and instructions for its use by the contract core lab. The investigational sites will then provide the device and instructions for use to the subject. The Event Monitor will be returned at the end of the subject's follow-up using shipping materials provided by the core lab.
- Cardioversions since last visit
- Heart failure status as assessed by NYHA classification at the time of visit
- Fluoroscopic Examination of Diaphragm Motion if the procedural examination indicates diminished phrenic nerve response
- Anticoagulation Monitoring: For subjects on anticoagulants, assessment of INR/PTT therapeutic levels as applicable/required (maintain as clinically indicated)
- Any additional ablation procedures performed
- Any hospital readmissions, including admission and discharge dates, since the previous visit
- Adverse Events

#### **5.12.6 90-Day Phone Call**

In case the 75-day follow-up visit and electroanatomical re-mapping procedure occur earlier than planned, the subject will be contacted by phone to collect information on any hospitalizations, repeat ablations, adverse events and/or symptoms of AF, AFL, or AT at 90 days post index procedure.

#### **5.12.7 6 Month Follow-up**

Subjects will return for an office visit 6 months (180 days  $\pm$  30 days) post-ablation treatment. At a minimum, the following data will be collected at 6 months:

- Medications including use, changes in or discontinuation of anticoagulation, rate control and/or antiarrhythmic medications
- Cardiac rhythm as determined by a 12-lead ECG at the time of the visit
- Cardiac rhythm as determined by a 24-hour continuous ECG monitor. ECG data from this monitor will be analyzed by a contract core lab. Investigational sites will be provided with the continuous ECG monitor device and instructions for its use by the contract core lab. The investigational sites will then provide the device and instructions for use to the subject. The device will be worn by the subject for a single 24-hour period and then returned to the core lab with shipping materials provided by the core lab.

- Event Monitor provided at the 75-day follow-up visit will be reviewed for weekly scheduled and ad hoc symptomatic monitoring. ECG data from this monitor will be analyzed by a contract core lab.
- Cardioversions since last visit
- Heart failure status as assessed by NYHA classification at the time of visit
- Fluoroscopic Examination of Diaphragm Motion if the procedural examination indicates diminished phrenic nerve response
- Anticoagulation Monitoring: For subjects on anticoagulants, assessment of INR/PTT therapeutic levels as applicable/required (maintain as clinically indicated)
- Any additional ablation procedures performed
- Any hospital readmissions, including admission and discharge dates, since the previous visit
- Adverse Events

#### **5.12.8 12 Month Follow-Up**

Subjects will return for an office visit 12 months (365 days  $\pm$  30 days) post-ablation treatment. At a minimum, the following data will be collected at 12 months:

- Medications including use, changes in or discontinuation of anticoagulation, rate control and/or antiarrhythmic medications
- Cardiac rhythm as determined by a 12-lead ECG at the time of the visit
- Cardiac rhythm as determined by a 24-hour continuous ECG monitor. ECG data from this monitor will be analyzed by a contract core lab. Investigational sites will be provided with the continuous ECG monitor device and instructions for its use by the contract core lab. The investigational sites will then provide the device and instructions for use to the subject. The device will be worn by the subject for a single 24-hour period and then returned to the core lab with shipping materials provided by the core lab.
- Event Monitor provided at the 75-day follow-up visit will be reviewed for weekly scheduled and ad hoc symptomatic monitoring. ECG data from this monitor will be analyzed by a contract core lab. The Event Monitor will be returned at the end of the subject's follow-up using shipping materials provided by the core lab.
- Cardioversions since last visit
- Heart failure status as assessed by NYHA classification at the time of visit
- Fluoroscopic Examination of Diaphragm Motion if the procedural examination indicates diminished phrenic nerve response

- Anticoagulation monitoring: For subjects on anticoagulants, assessment of INR/PTT therapeutic levels as applicable/required (maintain as clinically indicated)
- Any additional ablation procedures performed
- Any hospital readmissions, including admission and discharge dates, since the previous visit
- Adverse Events

### 5.13 Unscheduled Visit

Any unscheduled follow-up visits that occur throughout the study, other than routine follow-up visits per the institution's or investigator's normal standard of care, shall be documented. At the minimum, the following data will be collected:

- Medications including use, changes in or discontinuation of anticoagulation, rate control and/or antiarrhythmic medications
- Cardiac rhythm as determined by a 12-lead ECG at the time of the visit
- Event Monitor provided at any previous follow-up visit will be reviewed for weekly scheduled and ad hoc symptomatic monitoring. ECG data from this monitor will be analyzed by a contract core lab.
- Cardioversions since last visit
- Heart failure status as assessed by NYHA classification at the time of visit
- Anticoagulation monitoring: For subjects on anticoagulants, assessment of INR/PTT therapeutic levels as applicable/required (maintain as clinically indicated)
- Any additional ablation procedures performed
- Any hospital readmissions, including admission and discharge dates, since the previous visit
- Adverse Events

### 5.14 Study Exit or Premature Withdrawal

Once the subject has completed the final follow-up visit they can be exited from the study provided that they do not have any conditions that require continued follow-up.

If a patient withdraws from the study prematurely or is withdrawn based on the judgement of investigator, the site will document the reason for withdrawal and inform the Sponsor. These patients will continue to be followed for safety through the 12-month timepoint.

## 5.15 Schedule of Study Assessments

**Table 4: Summary of Study Assessments**

Assessment	Baseline	Procedure	PreDischarge / 7 Days	30 Days Post-Procedure/ Discharge*	75 Days	90 Days****	6 Month	12 Month	Unscheduled
Visit Timeframe (days)			7±2	30±7	75±15	90 ±7	180±30	365±30	-
Medical History	X								
Medication History (current)	X								
Medications		X	X	X	X		X	X	X
Pregnancy test (for females of childbearing potential)	X	X			X				
12-lead ECG	X		X	X	X		X	X	X
24-Hour Continuous ECG Monitor (e.g., Holter)							X	X	
Cardiac CT or MRI	X				X				
TEE or other imaging modality (to exclude left atrial thrombus)	X								
Electroanatomical Mapping		X			X				
Event Monitor					X		X	X	X
Record DC Cardioversions at Discharge or since Last Visit			X	X	X	X****	X	X	X
NYHA Classification	X		X	X	X		X	X	X
Fluoroscopic Examination of Diaphragm Motion		X			X***		X***	X***	
Anticoagulation Monitoring	X**	X**	X**	X**	X**		X**	X**	X**
Adverse Events		X	X	X	X	X****	X	X	X
Phone Consultation						X****			

\* Whichever is later

\*\* INR or PTT (as applicable for patient on heparin or NOACs); ACT for procedural monitoring

\*\*\*\*If the procedural study indicates decreased phrenic nerve function

\*\*\*\*If the 75-day follow-up occurs earlier than planned; the patient will be contacted for a telephone follow-up consultation..

## 6. Risk Benefit Assessment

The Sponsor has conducted an analysis of the benefits and risks of the FARAPULSE Endocardial Ablation System and ablation procedure as described below. The conclusion of this review is that the subject investigation is justified because the overall potential benefit to the population outweighs the risks.

### 6.1 Risks

The risk profile associated with the FARAPULSE Endocardial Ablation System and the ablation procedure is expected to be consistent with similar devices currently in clinical use for percutaneous cardiac ablation for treatment of paroxysmal atrial fibrillation.

#### 6.1.1 Potential Adverse Events

The following anticipated adverse events have been identified as possible complications of percutaneous atrial fibrillation ablation procedures and these and others may be associated with the FARAPULSE Endocardial Ablation System:

- Access site complications (e.g., hematoma, pseudo-aneurysm)
- Air embolism
- Anemia
- Arrhythmia, potentially requiring cardioversion, defibrillation, or rhythm management device
- Arteriovenous fistulae
- Back pain
- Bed sores
- Bleeding, hematoma, hemorrhage or aneurysm at vascular access sites
- Blood pressure changes including hypotension or hypertension
- Coronary artery or vein injury
- Cardiac tamponade
- Cardiac arrest or cardiac failure
- Catheter entrapment
- Cardiogenic shock
- Conduction system injury resulting in sinus arrest or heart block, either transient or permanent
- Congestive heart failure
- Death
- Drug allergic reaction or side effects (e.g., from contrast, steroids, analgesics, anesthetics, anticoagulants, sedatives, etc.)
- Esophageal injury, ulcer or fistula
- Hemorrhage
- Hemodynamic compromise
- Hemopericardium
- Hemoperitoneum

- Hemothorax
- Local infection, systemic infection, and/or sepsis
- Myocardial infarction / transient ischemia
- Nerve damage
- Organ failure
- Pain
- Perforation (e.g., of diaphragm, heart, liver, lung, and/or vessels).
- Pericardial irritation
- Pericardial effusion
- Pericarditis
- Peritonitis
- Phrenic nerve injury
- Pneumomediastinum
- Pneumopericardium
- Pneumoperitoneum
- Pneumothorax
- Pulmonary vein injury or stenosis
- Risk of cancer or birth defect/harm to fetus from x-ray exposure
- Skin burns/irritation from x-ray exposure
- Stroke/transient ischemic attack
- Surgical or open-heart surgery to remove retained catheter
- Thrombosis
- Thromboembolism
- Vessel damage, dissection, or occlusion.

## 6.2 Benefits

The FARAPULSE Endocardial Ablation System is a Pulsed Electric Field (PEF) ablation system that produces continuous transmural cardiac lesions to treat atrial fibrillation using an ablation procedure that is similar to other commercially available percutaneous ablation catheters. More specifically:

- The device system is used during percutaneous endocardial ablation procedures like other commercially approved catheter systems.
- The device system is composed of similar biocompatible materials.
- The device system is a non-thermal ablation technology with targeted cardiac tissue specific mechanism of ablation.
- The device uses the standard percutaneous techniques for ablation procedures.
- The device utilizes a standard irreversible electroporation generator to deliver energy in the form of ablation dose.

A fundamental difference between the FARAPULSE Endocardial Ablation System and other commercially approved atrial fibrillation ablation systems is that the Pulsed Electric Field or irreversible electroporation energy is delivered through

electrodes embedded in the endocardial ablation catheter for delivery of such energy in the pulmonary veins.

As such, the potential risks are roughly equivalent to those associated with commercially released systems being used for percutaneous cardiac ablation procedures. Currently, the complication rates for commercially available catheters are low and have declined as physicians have continued to learn more about cardiac ablation techniques. Furthermore, FARAPULSE, Inc. has conducted bench and in-vivo testing to ensure safe use of the device during clinical investigation and is in compliance with the applicable requirements of the Medical Device Directive 93/42/EEC.

There are no *guaranteed* benefits from participation in this study. Information gained from the conduct of this study may also be of benefit to other persons with the same medical condition.

## 7. Statistical Analysis and Endpoint Assessment

### 7.1 General Statistical Considerations

The primary objective of this study is to further characterize the safety and feasibility of the FARAPULSE Endocardial Ablation System in subjects with paroxysmal atrial fibrillation.

This is a feasibility study with no formal hypothesis testing and therefore no required sample size. Study results will be presented using descriptive statistics. Results from this study will be used to inform and design additional clinical studies.

All subjects will be followed on an Intent-to-Treat basis. The device performance will be assessed based on an intent-to-treat analysis of the primary safety and feasibility endpoints, and secondary feasibility endpoints. A per protocol analysis, along with other secondary analyses, will also be reported.

An intent-to-treat analysis of device performance will be assessed as the number of patients in whom all pulmonary veins are electrically isolated using only the study device at the completion of the index procedure.

All subjects who meet enrollment criteria for the study and undergo catheterization and ablation procedures with the FARAPULSE Endocardial Ablation System shall be included in the Intent-to-Treat cohort/population. This will exclude any patients in whom exclusion criteria were identified prior to any ablation with the study device.

Demographic, baseline clinical and disease characteristics, procedural results and primary, secondary and all additional endpoints will be summarized using descriptive statistics.

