#### 4.4 System Components: FARAPULSE Endocardial Ablation System

The FARAPULSE Endocardial Ablation System used in the subject clinical investigation consists of the FARAWAVE Endocardial Ablation Catheter System, the FARASTAR Endocardial Generator System, and the FARADRIVE Deflectable Sheath System (**Figure 1**). Model (REF#) numbers of the components used in this study are detailed in **Table 2**.

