## 5.3 Study Endpoints

### 5.3.1 Primary Safety Endpoint

The primary safety endpoint for this study is the Composite Safety Endpoint (CSE) defined as the incidence of the following early-onset and late-onset serious adverse events (SAEs) which are device- or procedure-related:

Early onset (within 30 days of any endocardial ablation for atrial fibrillation)

- Death
- Myocardial infarction (MI)
- Persistent diaphragmatic paralysis
- Stroke or transient ischemic attack (TIA)
- Peripheral or organ thromboembolism
- Pericarditis
- Cardiac tamponade / perforation
- Vascular access complications
- Hospitalization (initial or prolonged)\*
- Heart block

Late onset (any time during follow-up)

- Pulmonary vein (PV) stenosis (> 70% diameter reduction from baseline)
- Atrio-esophageal fistula

\* Excludes hospitalization (initial & prolonged) solely due to arrhythmia (AF/Atrial Flutter/Atrial Tachycardia) recurrence or due to non-urgent cardioversion (pharmacological or electrical). Hospitalization excludes visits to hospital-associated outpatient facilities such as clinics or emergency wards.

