#### **5.8 Enrollment**

Subjects that meet all of the eligibility criteria and are deemed suitable by the investigator will be invited to participate in the study.

Subjects will be considered enrolled at the time of signing the Informed Consent Form.

Each subject will be assigned a unique study identification code to protect each subject's confidential health information. The unique study identification code will not include date of birth or subject's first and last initials and will be used to link study data and other study information to the subject in lieu of the subject name. The Subject Name Log will be used to link the unique study identity code to the subject and will be maintained at the site. This log will remain confidential and will not be provided to the Sponsor, but only used for reference when monitoring at the study site.

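### Section 7.1 leaves unclear whether a procedure started but ended before any study-device ablation counts in Acute Procedural Success and the primary safety composite

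*Combined protocol and SAP*

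**What the plan says.** Section 7.1 names the endpoints analysed by intent to treat: "The device performance will be assessed based on an intent-to-treat analysis of the primary safety and feasibility endpoints, and secondary feasibility endpoints". It then defines the Intent-to-Treat set: "All subjects who meet enrollment criteria for the study and undergo catheterization and ablation procedures with the FARAPULSE Endocardial Ablation System shall be included". The next sentence removes one group: "This will exclude any patients in whom exclusion criteria were identified prior to any ablation with the study device".

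Other sections bear on how this is read:

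- Section 5.8 fixes enrollment at consent: "Subjects will be considered enrolled at the time of signing the Informed Consent Form". The Intent-to-Treat set is therefore narrower than the enrolled set.
- Section 4.4 says that the investigational system "consists of the FARAWAVE Endocardial Ablation Catheter System, the FARASTAR Endocardial Generator System, and the FARADRIVE Deflectable Sheath System".
- Section 5.12.2 puts femoral access, transseptal puncture, the sheath, the pacing catheters, a baseline assessment, catheter deployment and pacing capture before any energy is delivered. Of the sheath it says: "The FARADRIVE Deflectable Sheath will then be prepared and advanced via guidewire to the left atrium".
- Sections 5.3.1 and 7.6.1 and the Executive Summary define the early-onset part of the CSE as "Early onset (within 30 days of any endocardial ablation for atrial fibrillation", and count device- or procedure-related serious events.
- In Table 3, the tamponade/perforation entry is tied to the index ablation procedure and includes events during it.

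No section defines an attempted-procedure or safety population. None says how a procedure that ends before ablation scores for APS.

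**The concern.** In a feasibility study, failing to reach ablation because of failed access, a device or generator fault, or a complication is itself a feasibility result. A serious procedure-related event before ablation is a safety result. Vascular access complications and tamponade are CSE components that access alone could cause.

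If Intent-to-Treat membership requires delivered ablation, both results can leave the primary endpoints while the label suggests that nobody has been dropped. No hypothesis test depends on this. However, section 7.2 says that the estimates and their confidence intervals are the purpose of the sample and will inform the powering of a later pilot study. An APS that is conditional on ablation, carried forward under an intent-to-treat label, would be optimistic whenever aborts occur. Two analysts could also build different primary denominators from the same sentence.

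**Working it through.** **Reading the text.** The plan gives no figure to reproduce: 80 is a cap, and section 7.1 disclaims formal testing. The table sets the two readings side by side.

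| Subject | Literal reading (ablation delivered) | Looser reading (session begun) |
|---|---|---|
| Ablated, veins not isolated | In, APS failure | In, APS failure |
| Stopped before ablation by a complication, failed access or a fault | Out of APS and CSE | In |
| Found ineligible after access, before ablation | Out of APS and CSE | Out of APS and CSE |

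The window question is separate. For an ablated subject there is no gap: this protocol also uses 'within' looking backwards (exclusion criterion 5, for example), so events during access are covered. A session completed only with a commercial ablation device also has a start date, because the window refers to any endocardial ablation. A subject never ablated at all has none, apart from what Table 3 supplies for tamponade.

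**Size.** Intervals are exact (Clopper-Pearson) two-sided 95%. That method is an assumption, since the plan names none for proportions. All abort and event counts below are also assumptions.

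Scale of plausible aborts: section 3.4.1 describes 38 + 16 = 54 endocardial patients and mentions no abort. If that is read as 0/54, the upper limit is 1 - 0.025^(1/54) = 6.6%, and 0.066 x 80 = 5.3, or about 5 of 80.

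APS with n = 80 started, a aborts (none for ineligibility), and every ablated subject isolated. The literal set gives (80 - a)/(80 - a); the started set gives (80 - a)/80.

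| a | Literal set | Started set |
|---|---|---|
| 0 | 80/80 = 100% | 80/80 = 100% |
| 1 | 79/79 = 100% (95.4 to 100) | 79/80 = 98.75% (93.2 to 99.97) |
| 2 | 78/78 = 100% (95.4 to 100) | 78/80 = 97.5% (91.3 to 99.7) |
| 5 | 75/75 = 100% (95.2 to 100) | 75/80 = 93.75% (86.0 to 97.9) |

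The choice of starting point matters too. If 3 of 5 aborts come before the study device is inserted, APS over device-inserted subjects is 75/77 = 97.4% (90.9 to 99.7), against 93.75% over started procedures. If 1 of 2 aborted subjects is removed for ineligibility, APS is 78/79 = 98.7% (93.2 to 99.97).

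CSE, with k events among ablated and j among aborted subjects: the literal rate is k/(n - a) and the started rate is (k + j)/n. Multiplying out, (k + j)/n > k/(n - a) holds only when j/a > k/(n - a). With a = 2:

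| k | Literal set | Started, j = 0 | Started, j = 1 | Started, j = 2 |
|---|---|---|---|---|
| 0 | 0/78 = 0% (upper 4.6) | 0/80 = 0% (upper 4.5) | 1/80 = 1.25% (0.03 to 6.8) | 2/80 = 2.5% (0.3 to 8.7) |
| 2 | 2/78 = 2.56% (0.3 to 9.0) | 2/80 = 2.50% (0.3 to 8.7) | 3/80 = 3.75% (0.8 to 10.6) | 4/80 = 5.0% (1.4 to 12.3) |

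The CSE event count can therefore only fall under the literal set. The rate can go either way: with k = 2 and j = 0 the literal set gives the slightly higher rate.

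**The case against.** The strongest reply is that section 7.1 does not exclude aborted procedures at all. Its sentence on patients found ineligible before study-device ablation would do almost no work if delivered ablation were already a condition of membership. Section 5.12.2 uses the term for the whole session, starting with anesthesia: "FARAPULSE endocardial ablation procedure patients will undergo anesthesia according to institutional protocol". Table 3 also shows that, for tamponade, the sponsor had the index procedure in mind, including events during it. This stands to the extent that the text is ambiguous. A reader might infer that the plan clearly drops every aborted case, and the documents do not support that. Equally, nothing in them settles the matter the other way, and Table 3 helps with one component only.

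A second reply is that no effect has been shown. This also stands. Section 3.4.1 reports that all pulmonary veins were isolated with the study device at the end of the index procedure in both endocardial studies, and every abort count above is assumed. Five of 80 is the edge of what 0/54 allows, not an expectation.

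A third reply is that the harm is not lost. That is correct. Section 8.2 collects adverse events from enrollment, section 10.10 has procedure-related and serious events adjudicated and safety data reviewed by the monitoring board, and section 11.2.2 requires exit forms for all enrolled subjects. Secondary safety endpoint 1 would still capture these events, because section 7.1 ties only the primary endpoints and the secondary feasibility endpoints to this set. What is at risk is attribution to the primary endpoints, not the data.

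Finally, scoring every started but non-ablated subject as an APS failure would override the exclusion that section 7.1 states for patients found ineligible. The fix has to respect that rule.

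**Conclusion.** The definition is ambiguous and should be settled before analysis. On the literal reading, procedures ended before ablation leave both primary endpoints. On the looser reading two smaller gaps remain: a patient found ineligible after access has begun leaves the CSE even if access caused a serious event, and the early-onset window has no start date for a never-ablated subject, tamponade partly excepted.

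Excluding such subjects can only raise APS, by 1.25 percentage points for each assumed abort in 80 when all ablated subjects are isolated. It can only lower the CSE event count. A reader might infer that the CSE rate is biased downwards. That does not follow, since it is understated only if the event proportion is higher among aborted than among ablated subjects. With no aborts nothing changes.

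Severity is minor to moderate: the study is descriptive and data collection is intact, but the estimates feed the planning of a later study.

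**What to change.** 1. In section 7.1, define the primary set for the CSE as all enrolled subjects in whom the study procedure is started, taken as first venous access. Include those found ineligible during the procedure.
2. For APS, use the same set minus subjects found to meet an exclusion criterion before any study-device ablation, which keeps the rule already stated. Count the remaining subjects without study-device ablation as APS failures. Also report APS over subjects in whom the study device was inserted, because transseptal access uses commercial tools (section 5.12.2). Say which component defines insertion, since section 4.4.3 allows a commercial sheath.
3. Keep the ablated-only set as supportive, labelled 'treated'.
4. For never-ablated subjects only, run the CSE 30-day window from the index procedure date, in line with the tamponade entry in Table 3. Reconcile section 5.12.4, which times the 30-day visit from ablation, with Table 4, which heads it as post-procedure.
5. List non-ablated subjects with reasons and events.

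The cost is a small wording amendment, which may need Ethics Committee and Competent Authority approval under section 11.3. No new form is needed. APS or CSE figures may look slightly less favourable.
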